6.2 SAMPLE SIZE DETERMINATION

This is a proof-of-concept study. There are no studies in the literature to provide reliable estimates of active treatment or placebo response rates using vomiting/retching events, or the estimate of variances around these measures, in participants with CVS being treated acutely with an abortive therapy. Consequently, sample size was not based on power calculations.

Approximately 150 participants will be randomized to 1 of 3 treatment groups. An N of 50 per group should be sufficient to describe and compare across the efficacy parameters.

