5.3 DESIGN

This is a multicenter, randomized, double-blind, parallel group, placebo-controlled, efficacy and safety study of adult outpatients diagnosed with CVS and experiencing recurring episodes of stereotypical vomiting. Participants meeting all inclusion criteria and none of the exclusion criteria will be randomized to treatment with either 1 mg AZ-010, 3 mg AZ-010, or placebo in a 1:1:1 ratio (active:active:placebo). Each randomized participant will receive training in the use of the Staccato device and detailed instructions for the use of the ePD in the clinic as well as undergo a pre-test self-administration of their randomized study medication. Each participant will be monitored during a 2 hr. observation period and have 12-lead ECG (triplicate) assessments at pre-dose and 2, 30, 60, 90, and 120 minutes post dose. If there are no clinically-significant observations or abnormalities on the ECG, including QT prolongation, the participant will be provided with their Patient Kit that contains the remaining 5 unused Staccato devices in addition to the 1 Staccato device that they

used in the clinic. Up to 5 administrations of study medication will be allowed in an At Home environment. CVS patients between 18 and 60 years of age who have experienced at least 3 episodes of recurrent vomiting in the last 12 months and 2 episodes in the last 6 months (with stereotypical episodes of acute onset vomiting lasting <1 week and absence of vomiting between episodes) are eligible for participation. Approximately 50 participants will be randomized to each of 3 treatment groups: 1 mg AZ-010, 3 mg AZ-010, or matching Staccato Placebo (Staccato device without drug coating). Randomization will be stratified by duration of the participant's typical CVS episode into one of the following two categories: 1) Typical episode of CVS lasts 24 hrs. or less from the first vomiting/retching event; 2) Typical episode of CVS lasts greater than 24 hrs. from the first vomiting/retching event.

There will be 3 Research Clinic visits and a home treatment period, as indicated in the Study Schema (5.4).

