Randomized participants without clinical observations in the 2-hour observation period will be asked to treat a subsequent CVS episode (with single daily dosing up to 5 consecutive days) within 12 weeks after the randomization date. Enrolled participants will self-administer the study medication when they know their CVS episode is imminent or as soon as possible after a CVS-related vomiting episode has begun. Participants will interact with their ePD prior to initiation of treatment (if possible) and to capture the study data. The ePD will be used to record the date and time of study medication administration, the number of vomiting and retching events, and the participant reported outcome measures (including the intensity and duration of the CVS episode, severity of abdominal pain, nausea, and anxiety/panic, and characteristics of the nausea, vomiting and retching over defined time periods) (section 5.8). Participants will also record the number of vomiting and retching events in the 24 hours after dosing on a paper questionnaire.

Participants will be instructed to contact the Research Clinic at the earliest possible time after initiation of dosing and at any time should they require rescue medication, medical assistance or experience an intolerable AE at home during the treatment period. Participants will record rescue medications taken after administration of study medication in their ePD and on a paper concomitant medications form. Rescue medication may include any agent(s) from the list described in Section 9.8 of the protocol. Participants are encouraged to avoid rescue medication for the first 2 hrs. following treatment with the study medication.

Participants will be required to return to the Research Clinic (Visit 3) within 3-5 days from the last study medication administration for final in-clinic assessments, to return the Patient Kit containing the used and unused study medication, ePD, and any other unused supplies. Conversely, participants will be asked to return to the Research Clinic after 12 weeks with their unused Patient Kit if they did not treat a CVS episode within this time period.

Visit 3 will include the following assessments: Vital signs; full physical examination; assessment for treatment emergent adverse events; 12- lead ECG, concomitant medications (including rescue medication taken), and clinical labs.

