6 STATISTICAL ANALYSES

6.1 GENERAL CONSIDERATIONS

All analysis dataset preparations and statistical analyses will be performed using SAS[®] version 9.4 or higher. No imputation will be performed for missing data unless stated otherwise.

Data will be summarized by dosing group (1 mg AZ-010, 3 mg AZ-010, placebo). All data for analysis will be listed by participant.

The same number of decimal places as in the raw data will be presented when reporting minimum and maximum, 1 more decimal place than in the raw data will be presented when reporting mean and standard deviation.

Continuous variables will be summarized by treatment using descriptive statistics (n, mean, median, standard deviation, minimum, and maximum). For categorical variables, frequencies and percentages will be presented by treatment. Baseline is defined as the last observation prior to initiation of Study Medication.

Listings for CSR Appendix 16.2 will include all the participant data points being collected or derived for analyses. Data listings will be provided for all participants up to the point of study completion or withdrawal.

All statistical tests will be 2-sided with a significance value of 0.05. Participants will generally be summarized by actual treatment received.

If the 12-week treatment period has expired and participants have not yet treated a CVS episode, they will be excluded from efficacy analyses since they did not receive any study medication specifically in anticipation of a CVS episode.

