6.9.1.4 POPULATION-LEVEL SUMMARY

Mean number of vomiting retching events in the first 2 hours following the initial treatment (during the Home Treatment Period) from an analysis of variance model, with treatment group and randomization strata in the model.

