6.10 MAIN ANALYTICAL APPROACH

Data from the RINVR, IAS, VAS, and PES will be analyzed using a mixed model for repeated measures (MMRM). Fixed effects will include treatment group, timepoint, randomization strata, and a treatment-by-timepoint interaction. Timepoint will be fit as a repeated effect using the repeated statement in SAS. An unstructured covariance structure and Kenward-Roger degrees of freedom will be used. In the event an unstructured covariance structure fails to converge, a Toeplitz structure will be used.

Least squares means will be presented for treatment*timepoint, with the significance level of the treatment-by-timepoint interaction presented in summary tables. Pair-wise comparisons of differences in LS means, two-sided 95% confidence intervals (CIs) on differences, and p-values will be provided for each active treatment versus placebo for each timepoint.

Proportion data (ie, rescue medication or visits to urgent care/ER/doctor will be analyzed using a Mantel-Haenszel test, stratifying on randomization strata, in a pairwise fashion of each dose versus placebo.

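### Does calling 50 per group sufficient, with no precision figure and no stated interval for the primary and proportion comparisons, leave the results uninterpretable?

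*Combined protocol and SAP*

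**What the plan says.** SAP 6.2 and protocol 12.3 say the same thing. The trial is a proof of concept, no reliable response or variance estimates exist, and the sample size does not come from a power calculation. SAP 6.2 then adds: "An N of 50 per group should be sufficient to describe and compare across the efficacy parameters".

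The 50 is a randomised number. SAP 5.3: "Approximately 50 participants will be randomized to each of 3 treatment groups". The efficacy set is smaller if some participants never treat an episode at home. SAP 5.3 has such people return after 12 weeks "with their unused Patient Kit if they did not treat a CVS episode within this time period", and SAP 6.1 says "they will be excluded from efficacy analyses since they did not receive any study medication specifically in anticipation of a CVS episode". SAP 6.9.1.3 also removes those stopped after the in-clinic ECG. Protocol 8.3 does not replace withdrawals.

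On outputs, SAP 6.9.1.4 defines the primary summary as a mean "from an analysis of variance model, with treatment group and randomization strata in the model". SAP 6.10 fits a repeated-measures model to the RINVR, IAS, VAS and Prior Episode data, and for that model says "two-sided 95% confidence intervals (CIs) on differences, and p-values will be provided for each active treatment versus placebo for each timepoint". Rescue use and care visits follow separately: the proportions "will be analyzed using a Mantel-Haenszel test, stratifying on randomization strata, in a pairwise fashion of each dose versus placebo". SAP 6.6 sets the primary hypothesis as AZ-010 (1 mg or 3 mg) against placebo.

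**The concern.** Two things seem to combine. First, the word sufficient has nothing behind it: no power, no variance, no interval width. The number that enters the efficacy analysis may also fall short of 50 by an amount the documents do not fix. Protocol 4.1 says the quiet phase between attacks can last several months, against a 12-week home period.

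Second, with no power basis, the interval around the treatment difference is what would show whether a non-significant result rules out a useful effect or is merely imprecise. Read literally, the SAP asks for that interval on the secondary scales but not on the primary endpoint, and not on the proportions. At stake would be the reading of a null primary result, which matters in a trial meant to guide the next development decision.

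**Working it through.** **The plan's own figure.** 3 groups × 50 = 150, as stated in SAP 5.2 and 6.2. Nothing further can be reproduced, because the plan gives no effect size, SD, response rate, power or target width. Alpha is 0.05 two-sided (SAP 6.1).

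**Precision implied by n.** The analysed n per group is an assumption, shown as a range. For a difference in means, the half-width in SD units is t(0.975, 2n−2) × √(2/n). For a difference in proportions, the largest half-width, with both proportions at 50%, is 1.96 × √(2 × 0.25/n).

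| Analysed per group | Means: half-width (SD) | Proportions: maximum half-width (points) |
|---|---|---|
| 50 | 1.984 × 0.200 = 0.397 | 19.6 |
| 40 | 1.991 × 0.224 = 0.445 | 21.9 |
| 30 | 2.002 × 0.258 = 0.517 | 25.3 |
| 25 | 2.011 × 0.283 = 0.569 | 27.7 |

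Using the residual degrees of freedom of the three-group model with one two-level stratum, 3n − 4, the means column becomes 0.395, 0.443, 0.513 and 0.564. The difference is immaterial.

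**What a smaller n does.** An observed difference of 0.4 SD gives 0.400 ± 0.397, or 0.00 to 0.80, with p = 0.048 at n = 50. At n = 25 it gives 0.400 ± 0.569, or −0.17 to 0.97, with p = 0.16. Under an assumed true difference of 0.5 SD, two-sample t-test power is 0.697, 0.478 and 0.410 at n = 50, 30 and 25. The chance of a non-significant result is therefore 30%, 52% and 59%. These figures show the cost of a smaller n. They are the same whether or not the SAP prints an interval.

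**Whether the interval can be recovered.** SAP 6.1 requires n, mean, median, SD, minimum and maximum by treatment for continuous variables, and frequencies and percentages for categorical ones. It also requires participant-level listings of all analysed data. SAP 8.1 requires the number treated in the at-home phase. From these:

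- Means: difference ± t × √(s₁²/n₁ + s₂²/n₂).
- Proportions: difference ± 1.96 × √(p₁(1−p₁)/n₁ + p₂(1−p₂)/n₂).

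For example, with an assumed SD of 4 events and 30 per group, the half-width is 1.96 × 4 × √(2/30) = 2.02 events in 2 hours. Over an assumed SD of 2 to 6, it is 1.01 to 3.04 events at n = 30 and 0.78 to 2.35 at n = 50. These intervals are unadjusted for the randomisation strata. The adjusted one differs to the extent that typical episode duration predicts the count.

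**Whether the adjusted interval needs a new analysis.** The planned ANOVA already contains treatment and strata. The LS-mean difference for each dose against placebo, with its standard error and 95% interval, is a contrast from that same fit. A stratified risk difference uses the same two-by-two tables as the planned Mantel-Haenszel test.

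**The case for a change.** The best case for a change starts from the order of priorities. The primary endpoint deserves at least the reporting given to the secondary scales, yet in the visible text only the scales get a stated difference and interval. Protocol 12.6.2 leaves the detail of efficacy tests to the SAP, and SAP 3 has the table shells follow the SAP, so this is the natural place to state the outputs. An interval derived by a reader is unadjusted, although randomisation and the model are both stratified. Adding the wording would take about three sentences and no new data or model.

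The observation about the text is correct: the interval sentence in SAP 6.10 is tied to LS means by timepoint, and the primary count is not in that model. The stronger claim, that sufficiency could never be checked or that a null result could not be interpreted, does not stand, because the required group summaries allow an approximate interval.

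Nor is absence from the whole plan shown. The SAP contents list has a section 13 on tables, listings and figures whose text is not in the available copy, and SAP 3 places the mock shells in a separate document.

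A precision sentence in 6.2 would add little. Half-widths in SD units depend on n alone, and with the variance unknown they do not say whether precision is adequate in vomiting events. The SAP is marked final on 3 March 2022, after the planned last-subject date of December 2021 in the protocol synopsis. Such a sentence would describe the sample size after the fact without justifying it.

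**Conclusion.** No change follows. The lack of a power basis is disclosed and explained, the stated numbers are consistent, and the word sufficient is loose wording that drives no analysis. The missing line on differences and intervals for the primary ANOVA and the Mantel-Haenszel comparisons is a reporting detail. A competent analyst would be expected to supply it from models and tables already specified, and following the plan as written still gives sound estimates and tests.

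The precision itself is modest: about 0.40 SD at 50 analysed per group and 0.57 SD at 25, and at most 20 to 28 percentage points for proportions. It depends on how many participants treat an episode, which the reporting wording cannot alter. The analysed numbers below 50, the SDs of 2 to 6 events and the 0.5 SD effect are assumptions for illustration; the documents give none of them. The conclusion also assumes that the summaries required by SAP 6.1 are produced for the efficacy endpoints.

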6.3 STUDY DATA

The study data to be analyzed include all clinical data captured by the case report form (eCRF) or otherwise centrally, including safety lab data and ECGs. The database will be locked for the final analyses.

6.4 ANALYSIS SETS

The following analysis populations are defined.

- Efficacy Population All participants who receive study medication and treated at least 1 episode of vomiting/retching due to their CVS, analyzed according to randomized treatment
- Safety Population All participants who receive study drug
- Per Protocol (PP) Population A PP population (subset of the Efficacy Population) may be decided upon which will exclude participants with important protocol deviations thought to potentially impact conclusions, if a sufficient number of participants with such deviations exist. If so, this population will be defined prior to breaking the blind.

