5.8.3 SECONDARY ENDPOINTS

All secondary endpoints will be evaluated based on the first vomiting/retching episode.

- The percentage of participants with no vomiting or retching events and no antiemetic benzodiazepine, or triptan rescue medication use in the first 24 hours following treatment. This endpoint will use incorporate data as captured in the 24 hour vomiting and retching questionnaire and the ePD.
- The intensity of the vomiting/retching attack (Intensity of Attack Scale) at 2, 6, 12, and 24 hours following treatment.
- The Rhodes Index of nausea, vomiting, and retching (RINVR) at 6, 12, and 24 hours following treatment.
- The assessment of abdominal pain at 2, 6, 12, and 24 hours following treatment (VAS 1-100; 0 = no pain and 100 = worst possible pain)
- The assessment of nausea at 2, 6, 12, and 24 hours following treatment (VAS 1-100; 0 = no nausea and 100 = worst possible nausea)
- The assessment of anxiety/panic at 2, 6, 12, and 24 hours following treatment (VAS 1-100; 0 = no anxiety/panic and 100 = worst possible anxiety/panic)
- The duration of the CVS episode at 24 hours in relation to their typical CVS episodes (Prior Episode Questionnaire)
- The intensity of the CVS episode at 24 hours in relation to their typical CVS episodes (Prior Episode Questionnaire)
- Use of rescue medication within the 24 hours following treatment with the study medication
- Visit to urgent care, emergency department, or physician's office for care related to the treated episode of CVS within the 24 hours following treatment with the study medication

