6.9 ENDPOINTS AND ESTIMANDS

6.9.1 PRIMARY ENDPOINT AND ESTIMAND

The mean number of vomiting/retching events in the 2 hours following treatment among those treated for a CVS episode (imminent or otherwise).

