6.9.1.1 TARGET POPULATION

The target populations are given by the Efficacy Population which include all participants treated during the Home Treatment Period for a CVS episode (imminent or otherwise). If a PP Population is defined, the primary analysis will be repeated for the PP Population.

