12.5 Analysis Populations

The Efficacy Population will include all patients who receive study medication and treated at least 1 episode of vomiting/retching due to their CVS. The Safety Population will include all patients who receive study drug. Patients will be summarized according to study medication dose received (i.e., as treated) should it differ from the randomized arm.

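### SAP 6.4 words the Efficacy Population more narrowly than SAP 6.9.1.1, and a flag built literally from 6.4 would drop prodromal dosers who never vomit

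*Combined protocol and SAP*

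**What the plan says.** SAP 6.4, the section that defines the analysis sets, puts in the Efficacy Population those who received study medication and "treated at least 1 episode of vomiting/retching due to their CVS, analyzed according to randomized treatment". Protocol 12.5 has nearly the same sentence: "The Efficacy Population will include all patients who receive study medication and treated at least 1 episode of vomiting/retching due to their CVS". Neither mentions an episode that is only imminent.

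SAP 6.9.1.1 says that the target population is given by the Efficacy Population, and describes that population as "all participants treated during the Home Treatment Period for a CVS episode (imminent or otherwise"). SAP 6.9.1 sets the primary estimand "among those treated for a CVS episode (imminent or otherwise").

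SAP 5.3 tells participants to "self-administer the study medication when they know their CVS episode is imminent or as soon as possible after a CVS-related vomiting episode has begun". A dose before any vomiting is therefore planned use. On the secondary endpoints, SAP 5.8.3 states: "All secondary endpoints will be evaluated based on the first vomiting/retching episode".

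**The concern.** The two SAP descriptions carry one name but, taken at their words, describe two sets. They differ on one kind of participant: someone who doses in the prodrome and then never vomits or retches. Under 6.9.1.1 this person is in, with a 2-hour count of 0. Under the words of 6.4 this person has treated no vomiting or retching and could be left out.

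Leaving them out would select on what happens after dosing. If the drug aborts attacks, more participants would be lost from the active arms than from placebo, and the lost ones carry the lowest possible counts. The same people would also be missing from the 24-hour endpoint of no vomiting and no rescue, which they could otherwise meet. Two workable readings of the primary analysis set also leave a choice that could be made after the data are seen.

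**Working it through.** **Step 1. Set the statements side by side.** The test case is a participant who took a home dose in the prodrome and never vomited.

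| Place | Who is in, or who is left out | Test case |
|---|---|---|
| SAP 6.4 | in: treated an episode of vomiting or retching | out, if read literally |
| Protocol 12.5 | same phrase as SAP 6.4 | out, if read literally |
| SAP 6.9.1.1 | in: treated at home, imminent attacks included | in |
| SAP 6.9.1 | in: same scope as 6.9.1.1 | in |
| SAP 6.9.1.3, intercurrent event 2 | in: had an attack needing treatment, imminent ones included | in |
| SAP 6.1 | left out: treated no attack in 12 weeks, because no drug was taken in anticipation of one | in |
| Protocol 7.6.3 | left out: took no study drug for an attack | in |

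Protocol 12.5 adds little to 6.4. It repeats the phrase, and SAP 3 says that the SAP supersedes the protocol's statistical section. The SAP has no rule saying whether 6.4 or 6.9.1.1 prevails, and 6.9.1.1 itself points back to the Efficacy Population.

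**Step 2. Can the test case occur?** Yes. Prodromal dosing is allowed (SAP 5.3). Inclusion criterion 4 asks for prodromal symptoms with about half of typical episodes. The 24-hour questionnaire (protocol 17.7) tells participants to enter 0 when nothing happens. Neither document says what share will dose in the prodrome, or how many of those will never vomit.

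**Step 3. What would the literal reading do?** The plan has no figure to reproduce: SAP 6.2 says that 50 per group was not based on a power calculation. All inputs below are assumptions:

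- f = share dosing in the prodrome, 0.25 to 0.75
- a = chance of never vomiting after a prodromal dose; placebo (aP) vs active (aA) 0.1 vs 0.3, 0.2 vs 0.5, or 0.2 vs 0.2
- m = mean 2-hour count in everyone else; 6 on placebo, and on active either 6 or 20% lower (0.8 × 6 = 4.8)

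Mean with all home dosers included = (1 − f·a)·m. Mean under the literal reading = m. Differences are active minus placebo.

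| f | aP, aA | All dosers, m 6 vs 6 | Literal | All dosers, m 6 vs 4.8 | Literal | Effect lost (m 6 vs 4.8) |
|---|---|---|---|---|---|---|
| 0.25 | 0.1, 0.3 | −0.30 | 0 | −1.41 | −1.20 | 15% |
| 0.25 | 0.2, 0.5 | −0.45 | 0 | −1.50 | −1.20 | 20% |
| 0.50 | 0.1, 0.3 | −0.60 | 0 | −1.62 | −1.20 | 26% |
| 0.50 | 0.2, 0.5 | −0.90 | 0 | −1.80 | −1.20 | 33% |
| 0.75 | 0.1, 0.3 | −0.90 | 0 | −1.83 | −1.20 | 34% |
| 0.75 | 0.2, 0.5 | −1.35 | 0 | −2.10 | −1.20 | 43% |

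First row: (1 − 0.075)·6 − (1 − 0.025)·6 = 5.55 − 5.85 = −0.30. With 4.8 on active: 4.44 − 5.85 = −1.41, and 1 − 1.20/1.41 = 15%.

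If all 50 per arm dosed at home, the last row would keep 50 × (1 − 0.15) = 42.5 on placebo and 50 × (1 − 0.375) = 31.25 on active.

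**Step 4. Direction.** The literal difference minus the all-dosers difference is f·(aA·mA − aP·mP). It is positive, hence toward no effect, when aA·mA exceeds aP·mP. With abort rates of 0.2 in both arms and m = 6 in both, both readings give 0. With 0.2 in both arms, f = 0.5 and m 6 vs 4.8, the all-dosers difference is 0.9 × (−1.20) = −1.08 against −1.20, so the literal reading would slightly enlarge the effect. A pull toward no effect needs active treatment to abort enough more attacks than placebo.

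**The case against.** The strongest reply is that the SAP already says who belongs. Section 6.9.1.1 names the Efficacy Population and includes imminent attacks, and 6.1, 6.9.1, 6.9.1.3 and protocol 7.6.3 agree. The documents also often use episode for the whole CVS attack and event for a single vomit or retch, and protocol 4.1 counts the prodrome as a phase of CVS. On that usage 6.4 simply means that a CVS attack was treated. This stands as evidence of intent. It does not remove the conflict, because the usage is not uniform: SAP 5.8.2 and 6.9.1.2 use episodes for the 2-hour count.

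A reader might infer more than the documents support:

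- *That the plan sets out to exclude its best responders.* The inclusive statements contradict this. Some who never vomit after a prodromal dose may have had attacks that would not have progressed in any arm.
- *That all zero counts are lost.* SAP 6.4 sets no time window. A prodromal doser with no events at 2 hours who vomits later stays in, as does anyone dosed after onset whose vomiting stops. Only those who never vomit are at risk.
- *That SAP 5.8.3 confirms the exclusion.* Its wording can be read as choosing the first treated attack, since protocol 7.6.3 may allow a second. Its own first endpoint counts participants with no vomiting, and SAP 6.9.2 handles intercurrent event 2 as for the primary estimand.
- *That the effect would vanish.* The zeros in the table follow from giving both arms the same mean in the retained participants. Nothing in the documents supports that input.

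**Conclusion.** SAP 6.4 and 6.9.1.1 contradict each other in wording on the primary analysis set. The intent is probably inclusive, so this is not a planned outcome-dependent exclusion. It remains worth correcting because 6.4 is where a programmer would look for the population flag, and applying it literally would make membership depend on outcome.

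The size cannot be estimated from the documents. Under the assumed rates the loss of effect is nil when abort rates are equal and the drug does nothing else. It is 15% to 43% when active aborts more attacks and also lowers counts by 20% in the rest, and complete when aborting attacks is the drug's only action. None of it arises if 6.9.1.1 is followed. This is a lesser point with a simple remedy.

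**What to change.** Amend the SAP before unblinding:

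- **6.4:** define the Efficacy Population as all randomised participants who took at least one home dose for a CVS episode, imminent or already under way, whether or not vomiting or retching followed, analysed as randomised.
- **6.4 or 6.9.1.2:** state that a recorded absence of events counts as 0. A blank entry is not a recorded absence and stays under 6.9.1.5.
- **5.8.3:** tie the secondary endpoints to the first treated CVS episode.

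The cost is a short SAP amendment, with no new data collection and no change to the planned models. Protocol 12.5 can stay as it is, because the SAP supersedes the protocol's statistical section. SAP 12, which already notes additions to the analysis populations, can record the clarification.
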